### 3. Research Work Plan

#### Aims:

The overall aim of this study is to examine the feasibility, acceptability, and preliminary effectiveness of our adapted PRC-COPC model “Siyakhana”. The main goal of this model is to increase engagement in HIV care for PLWH with SU and decrease HCW stigma towards SU.

Using a pilot hybrid Type 1 effectiveness-implementation design, we will explore whether our adapted Siyakhana model is feasible, acceptable, and potentially beneficial for improving engagement in health care for PLWH with SU, and reducing SUD stigma among HCWs. We will compare two matched COPC teams (i.e., similar in HCW makeup and patient population). Both COPC teams will provide treatment as usual, which we will enhance by providing a brief psychoeducational training on SU and SU screening (enhanced treatment as usual; ETAU). One of the COPC teams will also be randomized to receive the PRC model integration (described more below).

#### Study Sites

At the time of initial ethics submission, COPC teams were active in four clinics in the Western Cape: Asanda, Nomzamo, Ikhwezi, and Lwandle. Through ongoing conversations with Masincedane—the nonprofit organization that oversees these COPCs—Nomzamo and Ikhwezi were selected as our two COPC sites.

Both Nomzamo Community Health Centre and Ikhwezi Clinic are located within the larger community of Nomzamo, in the Helderberg Basin and Eastern Suburbs of the Cape Town Metropolitan Area. The clinics are located approximately 1.5km apart.

#### Study Design

The present study is a pilot study with the intent to establish the pilot effectiveness (not efficacy; primary), feasibility, and acceptability (secondary) of a PRC model (“Siyakhana”). The study uses a pilot hybrid Type 1 effectiveness-implementation design. In this study, a COPC team using our integrated Siyakhana PRC model will be compared to a COPC team without an integrated PRC.

Additional patient-level measures will be collected through this study (patient-level implementation) and NIDA grant R36DA057167 (patient-level stigma; PI: [name]). However, the primary focus of the present study is on the COPC staff level (i.e., HCW level).

#### Participants and Eligibility

##### 3.1.1 COPC HCW: Eligibility

A minimum of  $N=30$  HCWs will be enrolled in this study.

##### Rationale for Enrolment Numbers.

Exact enrollment numbers will depend on the size of each COPC team at the time of enrollment.

At the time of initial ethics submission—based on feedback from the Western Cape Department of Health—the largest COPC team was comprised of approximately  $n = 24$  HCWs (22 CHWs, 1 outreach team leader (supervisor; often a nurse by training), and 1 clinic-based nurse). The HCW numbers on each COPC may vary slightly at the time of enrollment due to staff members leaving and new hires. However, based on these numbers, we feel confident that each COPC team will employ at least  $n=15$  HCWs at the time of enrolment.

Therefore, we expect to enroll a minimum of  $N = 30$  HCWs (approximately 15 HCWs per COPC).

### **HCW Eligibility**

HCW eligibility criteria consists of:

*Inclusion:*

- Employed as a HCW (e.g., nurse, supervisor, CHW) for one of the COPC teams partnered with this study
- 18 years or older (expected for all HCWs employed by COPCs)

*Exclusion:*

- Unable or unwilling to complete informed consent and study procedures (i.e., brief trainings, self-report assessments) in English, isiXhosa, or Afrikaans

### **3.1.2 COPC Patient: Eligibility**

We aim to enroll  $N=50$  patient participants in this study ( $n=25$  patients per COPC team).

#### **Rationale for Enrolment Numbers.**

As this is a pilot study with the primary goal of establishing feasibility and acceptability, we view our effectiveness effect size as preliminary. However, based on prior work in this population and with PRCs, we expect to find a small improvement in patient re-engagement in care in enhanced treatment as usual (ETAU; previous studies have found about 14% re-engagement in ETAU) and a larger improvement in the PRC condition (previous studies have found 66-89% improvement). Assuming ETAU re-engages at an even higher rate (i.e., 24%), and Siyakhana (PRC condition) re-engages at the low end of previous studies (i.e., 66%), enrolling 50 patients will give us approximately 85% power to detect a difference in patient re-engagement after accounting for up to 20% attrition and/or missing records.

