### 1.2 Specific Objectives

To evaluate the feasibility, acceptability, and preliminary effectiveness of this PRC COPC integrated model (called “*Siyakhana*”), we will:

1. **Primary:** Evaluate the pilot effectiveness of *Siyakhana* reducing healthcare worker stigma towards substance use (SU), compared to a control condition (COPC enhanced treatment as usual (ETAU)):
  - a. Healthcare worker stigma towards SU at the three-month follow-up, measured using the Social Distance Scale (SDS;  $n=30$ )
2. **Secondary:** Evaluate the implementation of *Siyakhana* using the following measures:
  - a. Feasibility and Acceptability (COPC perspective)
    1. Feasibility and Acceptability subscales of an adapted Implementation and Dissemination measure, completed by healthcare workers (HCWs) in the *Siyakhana* condition at the six-month follow-up ( $n=15$ )
    2. Semi-structured qualitative interviews with HCWs in the *Siyakhana* condition after the six-month follow-up ( $n=15$ )
3. **Other:** Additionally evaluate the following outcomes using the following measures:
  - a. Feasibility and Acceptability (patient perspective)
    1. Feasibility and Acceptability subscales of an adapted Implementation and Dissemination measure, completed by patients (HCWs) in the *Siyakhana* condition at the three-month follow-up ( $n=25$ )
    2. Semi-structured qualitative interviews with patients in the *Siyakhana* condition after the six-month follow-up (up to  $n=25$ )
  - b. Feasibility and Acceptability (other stakeholder perspectives)
    1. Semi-structured qualitative interviews with key stakeholders (e.g., policymakers, organization and clinic heads, etc.,) at the end of the study (up to  $n=15$ )
  - c. Pilot effectiveness of *Siyakhana* patients (intervention) re-engaging in HIV care, compared to patients in the ETAU (control) condition, over three-months
    1. Patient engagement in clinic-based HIV care between baseline assessment and three-month follow-up assessment from medical records (dichotomous yes/no)

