## Study Procedures

### 3.1.1 COPC HCWs: Procedures

Study procedures for HCWs in the Pilot PRC Study are described below and illustrated in Figure 1.

**HCW Enrollment and Baseline Assessment:** Eligible and interested HCWs in the two partner COPC teams will be enrolled upon completed the informed consent process. All HCWs will then complete an individual baseline assessment consisting of self-report measures to assess basic demographic and job information, and stigma towards SUD (*primary*).

**COPC Randomization & Training.** After all HCW baseline assessments have been completed, one COPC will be randomly assigned to the ETAU condition (i.e., ETAU training only) and one COPC will be randomly assigned to the Siyakhana (i.e., ETAU and PRC integration training) condition. These trainings are described in more detail below.

[figure not shown]
Randomization will be determined by flipping a coin on a video-call with multiple study staff members (including at least one PI) in attendance.

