#### 4.1.2 Other Outcome: Patient Engagement in HIV Care

Throughout the study, patients' medical records will be monitored and clinic attendance data will be extracted.

We will compare the rate of re-engagement in HIV care in the Siyakhana condition to rate of re-engagement in HIV care in the ETAU condition. Our primary analysis will be a logistic regression examining re-engagement in care by group. We will examine engagement both between baseline and the 3MFU, and between baseline and the 6MFU. To supplement this dichotomous measure, we will also conduct a Poisson regression model to examine number of clinic visits by group over 3 and 6 months, and a Cox Proportional Hazard survival analysis to model time to re-engagement by group.

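### Is the stated power of about 85% for patient re-engagement too high for the planned logistic regression?

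*Combined protocol and SAP*

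**What the plan says.** Section 3.1.2 (COPC Patient: Eligibility) sets 50 patients, 25 "patients per COPC team". The rationale beneath it fixes the two rates: "Assuming ETAU re-engages at an even higher rate (i.e., 24%), and Siyakhana (PRC condition) re-engages at the low end of previous studies (i.e., 66" per cent). It then states the result: "enrolling 50 patients will give us approximately 85% power to detect a difference in patient re-engagement after accounting for up to 20% attrition". Records that cannot be found fall under the same allowance. The same paragraph says "we view our effectiveness effect size as preliminary", and it reports about 14% re-engagement under enhanced usual care and 66-89% with peer coaches in previous studies.

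Section 4.1.2 gives the analysis: "Our primary analysis will be a logistic regression examining re-engagement in care by group". Neither section gives a significance level or a number of sides, nor does section 4.1.2 say whether the group effect is tested by Wald or likelihood ratio.

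On the weight of this outcome, section 1.2 lists it under the third, Other, group of objectives: "Patient engagement in clinic-based HIV care between baseline assessment and three-month follow-up assessment from medical records (dichotomous yes/no"). The Study Design section says "the primary focus of the present study is on the COPC staff level (i.e., HCW level").

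**The concern.** This is the only power figure in the document, and it is the numerical argument for enrolling 50 patients. Most readers would take an unstated test to be two-sided at 5%. On that reading, the logistic regression with 20 evaluable patients per arm does not reach 85%. The chance of missing the assumed difference would be about 23-25% instead of 15%, and a null result would be read as stronger evidence than it is.

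**Working it through.** **Inputs.** From section 3.1.2: 25 enrolled per team, up to 20% loss, rates 0.24 and 0.66. Equal losses give 25 × 0.8 = 20 evaluable per arm. Alpha and sides are not in the document, so two-sided 5%, one-sided 5% and two-sided 10% are each tried as assumptions. Patients are treated as independent throughout.

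**Reproducing the stated figure (unpooled two-proportion z, two-sided 5%).** The standard error is √[(0.24×0.76 + 0.66×0.34)/20] = √(0.4068/20) = 0.1426. Then 0.42/0.1426 = 2.945, less 1.960 leaves 0.985, and Φ(0.985) = 83.8%. Summing the exact binomial probabilities of all outcomes in which this test rejects gives 84.6%. Either is a fair basis for a statement of approximately 85%.

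**Other closed forms, two-sided 5%, 20 per arm.**
- Pooled z: the mean rate is 0.45, so (0.42 − 1.960 × √(2×0.45×0.55/20))/0.1426 = (0.42 − 0.308)/0.1426 = 0.783, and power is 78.3%.
- Wald on the log odds ratio: ln(0.66/0.34) − ln(0.24/0.76) = 1.816, with standard error √[1/(20×0.1824) + 1/(20×0.2244)] = 0.705. Then 1.816/0.705 = 2.576, less 1.960 leaves 0.616, and power is 73.1%.

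**The planned logistic regression.** With group as the only covariate, power can be found exactly by enumerating both binomials.

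| Evaluable per arm | Test level | Wald | Likelihood ratio |
|---|---|---|---|
| 20 | two-sided 5% | 75.2% | 76.9% |
| 20 | one-sided 5% or two-sided 10% | 84.9% | 86.6% |
| 23 | two-sided 5% | 84.7% | 85.0% |
| 25 (no loss) | two-sided 5% | 86.1% | 89.4% |

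Exact power does not rise smoothly: at two-sided 5% the likelihood ratio test has 81.5% at 19 per arm and 76.9% at 20. Differences of a few points therefore carry little meaning.

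**Sensitivity to the assumed control rate (two-sided 5%, 20 per arm, 66% with the coach).** With 20% under enhanced usual care, power is 83.1% (Wald) and 85.6% (likelihood ratio). With the cited 14%, it is 88.9% and 94.8%. Four points of the ten-point cushion the plan added, 24% in place of 14%, are enough to bring power back to about 85%.

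**The case for a change.** The case for acting is that 85% holds only under conditions the plan leaves out, and that the choice moves power by about ten points. The unpooled z calculation, the only two-sided 5% method tried that comes close at 20 per arm, is not the analysis in section 4.1.2. It is also somewhat liberal at this size: its true type I error is about 7-8% when both rates lie between 30% and 50%. Section 5.1.10 says the study will inform later, powered trials, so its planning basis should be reproducible, and the cost is a sentence or two of text.

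The omission is real, and so is the 75-77% figure under its stated assumptions. Two things limit its weight. A two-proportion formula is normal planning practice for a logistic regression on one binary covariate, which makes the same comparison, so using one is not a mismatch in itself. And a replacement figure would be no firmer. By section 3.1.1 (COPC HCWs: Procedures), "one COPC will be randomly assigned to the ETAU condition (i.e., ETAU training only") and the other team receives the coach. Each arm is thus a single team, and every power figure here, the plan's or a substitute, rests on the same assumption of independent patients.

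**Conclusion.** The stated power is not shown to be wrong. It agrees with the planned regression at one-sided 5% or two-sided 10% (84.9-86.6%) and with a common approximation at two-sided 5% (83.8-84.6%). A shortfall of about 8 to 10 points (85 − 76.9 = 8.1; 85 − 75.2 = 9.8) arises only if one assumes two-sided 5%, the logistic Wald or likelihood ratio test, the full 20% loss split equally, and a 24% control rate. With 23 evaluable per arm, or a control rate near 20%, it largely disappears.

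What is left is missing detail in a planning sentence. It concerns an Other outcome in a pilot, the plan attaches no significance-based decision to it, and enrolment would stay at 50 on either reading. An analyst fitting the regression will report the odds ratio with its confidence interval, and that interval will show the precision achieved whatever power was stated beforehand. No change to the plan follows.

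### The 85% patient power and the by-group patient models ignore that one whole team is randomised to each arm, and the planned logistic regression would not reach 85% even with independent patients

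*Combined protocol and SAP*

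**What the plan says.** Under Aims, the design is set out: "We will compare two matched COPC teams". Under COPC HCWs: Procedures, a coin flip decides the allocation, so that "one COPC will be randomly assigned to the ETAU condition" and the other team receives Siyakhana. Patients are not randomised; they take the condition of the team that sees them. Under COPC Patient: Eligibility, the target is 50 patients, 25 "patients per COPC team".

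The Rationale for Enrolment Numbers for patients assumes 24% re-engagement under ETAU and 66% under Siyakhana, and concludes that "enrolling 50 patients will give us approximately 85% power to detect a difference in patient re-engagement". The figure is said to allow for losing as many as 20% of patients to drop-out or absent records. It gives no alpha, test, ICC or design effect. The same paragraph calls the effectiveness effect size preliminary.

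Section 4.1.2, which classes patient engagement as an Other outcome, states: "Our primary analysis will be a logistic regression examining re-engagement in care by group". It adds a Poisson model for the number of visits and a Cox model for time to re-engagement, both by group. No team effect, cluster-adjusted variance or related limitation appears there or elsewhere.

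**The concern.** With one team per condition, the difference between arms contains the intervention effect plus any difference between the two teams, their clinics and their patients. A calculation that counts patients as independently allocated includes only patient-to-patient variation. Its standard error is too small whenever teams differ, so its confidence interval is too narrow and a true null is rejected too often.

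Some between-team difference is plausible here. The outcome is attendance at clinic-based HIV care taken from medical records, and the teams work from different clinics. HCWs screen and refer patients after randomisation and training, so referral habits can shape the case mix of each arm. A nominally significant patient result could therefore reflect an ordinary difference between two clinics. A reader would also credit the design with a power that it does not have.

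**Working it through.** **Inputs from the documents.** p1 = 0.24, p2 = 0.66, 25 patients per team, up to 20% attrition, so m = 25 × 0.8 = 20 evaluable per team; one team per arm.

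**Assumptions, because the documents are silent.** Two-sided alpha 0.05; ICC of 0.01, 0.02 or 0.05.

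**Step 1: reproduce the 85% with independent patients.**

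- Unpooled z: SE = sqrt[(0.24×0.76 + 0.66×0.34)/20] = sqrt(0.4068/20) = 0.1426. Power = Φ(0.42/0.1426 − 1.96) = Φ(0.985) = 83.8%.
- Pooled z: the null SE at p = 0.45 is sqrt(2×0.45×0.55/20) = 0.1573. Power = Φ[(0.42 − 1.96×0.1573)/0.1426] = Φ(0.783) = 78.3%.
- Exact enumeration over the two binomial counts: logistic Wald test 75.2%, Pearson 76.9%, Fisher 66.6%.

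The unpooled z-test is the only two-sided variant tried that comes within two points of 85%. A one-sided pooled test gives 87.1%. The logistic regression that section 4.1.2 plans has about 75%, before any clustering.

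**Step 2: precision under between-team variation.** Design effect DE = 1 + (m − 1) × ICC = 1 + 19 × ICC. The interval should be sqrt(DE) times as wide, and the effective number per arm is 20/DE. The half-width for the risk difference at 24% and 66% is 1.96 × 0.1426 × sqrt(DE).

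| ICC | DE | Effective n per arm | CI width factor | Half-width |
|---|---|---|---|---|
| 0 | 1.00 | 20.0 | 1.00 | 0.28 |
| 0.01 | 1.19 | 16.8 | 1.09 | 0.30 |
| 0.02 | 1.38 | 14.5 | 1.17 | 0.33 |
| 0.05 | 1.95 | 10.3 | 1.40 | 0.39 |

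**Step 3: the unadjusted tests.** Beta-binomial enumeration with one team per arm, 20 patients each and nominal 5%. Type I error uses a common true rate of 45%, the mean of 24% and 66%.

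| ICC | Type I error, Wald / Pearson | Rejection at 24% vs 66%, Wald / Pearson |
|---|---|---|
| 0 | 3.9% / 4.4% | 75% / 77% |
| 0.01 | 6.0% / 6.7% | 73% / 76% |
| 0.02 | 8.2% / 9.0% | 72% / 74% |
| 0.05 | 14.9% / 16.2% | 68% / 72% |

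**Step 4: a test adjusted with a known ICC.** Putting 20/DE in place of 20 in step 1 gives the following power.

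| ICC | Unpooled z | Pooled z |
|---|---|---|
| 0.01 | 77% | 70% |
| 0.02 | 71% | 63% |
| 0.05 | 56% | 48% |

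These figures are optimistic because they treat the ICC as known. With one team per arm there are no degrees of freedom from which the trial could estimate it.

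**The case against.** The strongest case against is that this is a pilot, patient engagement is classed as Other, the Study Design section puts the primary focus on HCWs, and the effect size is called preliminary. Section 5.1.10 leaves powered effectiveness testing to later work, and no decision rule depends on patient significance. The teams are described as matched, and the Study Sites section puts their clinics about 1.5 km apart in one community, so the ICC may be small. At 0.01 the type I error is only 6-7%.

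All of that stands and limits the weight of the point. It does not remove it. The protocol chose to print a power figure and to plan inferential models. Calling the effect size preliminary does not tell a reader that the standard error omits team variation. Matching may reduce between-team differences, but it does not make them zero and gives no estimate of their size.

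A reader might infer that 85% is right if the ICC is zero. The documents do not support this: no test or alpha is given, and the analysis they name has about 75% power with independent patients. A reader might also infer that the planned test's chance of rejecting falls to 56% at an ICC of 0.05. That figure belongs to an ICC-adjusted test that is not planned. The planned unadjusted Wald test still rejects about 68% of the time; its main fault is excess false positives.

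**Conclusion.** The point holds. The stated power and the patient models make no allowance for between-team variation in a design with one randomised team per arm. The 85% is also at the favourable end without clustering: about 75% for the planned logistic Wald test, 77% for Pearson, 78% for a pooled z-test and 84% for an unpooled z-test.

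The direction of the clustering effect follows from the design. Its size rests on the assumed ICCs, and nothing in the documents favours one value in the range over another. The figures also assume two-sided 5%, 20 evaluable patients per team and, for type I error, a common rate of 45%.

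It would go too far to conclude that a design-effect correction makes the comparison sound. It shows what assumed variation would do to the interval, but team and condition remain fully confounded, so the interpretation has to be limited as well. Nor does this point bear on the HCW stigma outcome, whose analysis is a separate matter. The weight is moderate: the text should be corrected, and the design can stay as it is.

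**What to change.** **Rationale for Enrolment Numbers (patients).** Replace the 85% with a statement that, for 20 evaluable independent patients per team and two-sided 5%, power for 24% against 66% is roughly 75-84% depending on the test (Wald, Pearson, pooled or unpooled z), and about 75% for the planned logistic regression. Say that this ignores between-team variation. Add the adjusted-test range for ICC 0.01 to 0.05, which is 77% to 56% by unpooled z or 70% to 48% by pooled z, labelled as resting on assumed, known ICCs.

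**Section 4.1.2.** Report the re-engagement proportion in each arm and the difference, with the model-based interval. Beside it, give sensitivity intervals with the standard error multiplied by sqrt(1 + (m − 1) × ICC) for ICC 0.01, 0.02 and 0.05, where m is the number of evaluable patients per team. Apply the same caveat to the Poisson and Cox models. State that all patient comparisons are preliminary estimates conditional on these two teams, because with one team per arm the effects of team and condition cannot be separated.

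**Cost.** A few sentences and a few lines of analysis. The stated power and the intervals become less favourable. No extra patients, teams or data are needed.

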#### **Patient Eligibility.**

Patients will be eligible if they meet the criteria in the table below.

#### ***Patient Eligibility Criteria***

Inclusion Criteria	Exclusion
1. 18 years or older	1. Unable or unwilling to complete informed consent or study procedures in a language spoken by members of our team (i.e., English, isiXhosa, Afrikaans)
2. Living with HIV	
3. Problematic alcohol or other drug use (AOD) defined a CAGE score $\geq 2$	
4. Seen by a HCW from one of the COPC teams partnered with this study	

### **3.1.3 Stakeholders (Qualitative Interviews): Eligibility**

Participants will be up to n=15 HCWs (not previously enrolled in the study), leaders, policymakers or others involved in administration/supervision at COPCs, clinics, the Department of Health, or other relevant organizations.

### **Rationale for these numbers**

This number of participants will allow us to represent a wide range of perspectives. The study team will identify stakeholders by asking people working in the health care system to refer stakeholders that are involved in NGO managed COPC and CHW services. We anticipate this number will allow us to reach theoretical saturation for qualitative analysis.

